5. Participant has had a significant cardiovascular event (e.g. myocardial infarction, stroke) ≤ 6 months prior to screening visit; or stated history of congestive heart failure; or participant has evidence of cardiovascular disease assessed during the ECG at screening. In the event of a positive stress test, participants are referred to their primary care physician. If the electrocardiogram (ECG) is determined to be a false positive, participant may be allowed to participate in study after confirmatory records obtained.
6. Current infection (requiring prescription antimicrobial or antiviral medication, or hospitalization), or corticosteroid treatment (with the exception of inhaled or topical steroids) in the last 3 months prior to screening visit.
7. Participant is currently taking anti-inflammatory medication or has had anti-inflammatory medication within 1 week prior to screening (including over the counter formulations; e.g. Aleve, Motrin, ibuprofen, naproxen, low dose aspirin).
8. Surgery requiring >2 days of hospitalization in the last 3 weeks prior to screening visit.
9. Participant has an active malignancy (with the exception of basal cell) or autoimmune disease.
10. Participant has a chronic, contagious, infectious disease, such as active tuberculosis, Hepatitis B or C, or HIV, per self-report.
11. Participant is an amputee and/or has presence of partial or full artificial limb.
12. Participant currently has uncontrolled severe diarrhea, nausea or vomiting.
13. Participant has uncontrolled severe (including stage III or above) gastrointestinal absorption-related disorders, within 3 months of screening, such as: obstruction of the gastrointestinal tract, inflammatory bowel disease, short bowel syndrome, gastroesophageal reflux disease, gastroparesis, peptic ulcer disease, celiac disease, intestinal dysmotility, diverticulitis, ischemic colitis and bariatric surgery.
14. Cannot abstain from alcohol for the duration of the testing periods.
15. Subjects who fulfill any of the contraindications for MRI; examples include metal implants, devices, paramagnetic objects contained within the body and excessive or metal-containing tattoos.
16. Unable to participate in MR or DEXA assessments due to physical limitations of equipment tolerances (e.g., MRI bore size and DEXA 450-pound weight limit), claustrophobia, or based on Investigator's judgment at screening.

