Participants Recruitment and Screening

Males and females in the age ranges 65-90 years will be recruited from AdventHealth EMR, senior centers, television, radio, social media advertisements, text messaging, emailing, newsletters, and mass mailing lists from the Orlando, FL catchment area, and by contacting potential participants on the AdventHealth TRI's participant database.

Potential participants will be medically screened to determine good health and without any contraindication to exercise. Approximately equal numbers of men and women will be recruited. Neither race nor ethnicity will be exclusions.

We will recruit volunteers through public advertisement by placing advertisements in community newspapers and radio, as well as on social media. Individuals who respond to

the ads will be contacted by telephone for preliminary screening and will be given an opportunity to ask initial questions and be provided additional description of the study. Potential volunteers who seem to meet criteria will be scheduled for an outpatient examination at AdventHealth TRI. Informed, written consent will be obtained at the screening visit.

We anticipate ~400 phone screens to successfully enroll and complete 18 participants per group (anticipating 15 completers per group).

Consent Process

We attest that all study staff delegated the authority to obtain informed consent will follow “Investigator Guidance: Informed Consent (HRP-802)”, as well as “Investigator Guidance: Documentation of Informed Consent (HRP-803)”.

Non-English Speaking Participants

We will not be enrolling Non-English speaking participants due to the complexity of the visits, number of visits and length of the study. The participant population will be English speaking.

Participants who are not yet adults (infants, children, teenagers)

We are not enrolling participants who are not yet adults.

Cognitively Impaired Adults

We will not enroll cognitively impaired adults.

Adults Unable to Consent

We will not enroll adults who are unable to provide consent.

Documentation of Informed Consent Process

Documentation of the informed consent process is required to establish that the participant was accurately and adequately informed and that no study-related procedures were initiated prior to obtaining informed consent. A research team member will note in the source documentation the consent process, date consent was obtained, and that consent was obtained prior to initiating any research procedures.

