Waiver of Written Documentation of Consent or Waiver of Consent

N/A

Randomization

N/A

Study Visits

All study visits will be conducted at the AdventHealth Translational Research Institute.

PHASE I – SCREENING AND PRE-INTERVENTION TESTING

Both older athlete and older sedentary groups will undergo the screening and pre-intervention testing phase. See “Appendix: Schedule of Activities” for a table description of the procedures that will be performed during PHASE I.

Screening: SV1

Approximate visit time: ~ 3 1/2 hours

Volunteers will arrive, after an 8 hour overnight fast, to the AdventHealth TRI. Following voluntary written informed consent, all research participants will undergo a screening process for eligibility. This process may be repeated if necessary, under the discretion of the Medical PI. The following listed below procedures will be performed:

Demographics, Medication & Medical History, Physical Examination, Vital Signs, and Anthropometrics will be obtained. A full physical examination will be performed by a study physician, physician assistant, or nurse practitioner and will include general assessment of the following: head, ears, nose, eyes, throat, heart, lungs, abdomen, extremities, skin, neurological functioning, and any other impressions or problems noted by the provider at the time of exam. This will also include height, weight (metabolic), BMI, blood pressures, heart rate, respirations, temperature, medication, supplement history and a basic assessment of cognitive functioning via the Mini Mental State Examination (MMSE).

Electrocardiogram (ECG). A standard 12-lead ECG will be performed. Electrodes will be placed on the chest to provide a tracing of the electrical activity of the heart.

Physical activity questionnaires will be administered at screening. The Exercise History and Physical Activity Scale for the Elderly (PASE) are instruments that measures the level of habitual physical activity for individuals. The CHAMPS Physical activity health questionnaires will also be administered at screening. The MMSE will be administered at this time too.

Fasting blood draw to measure: a lipid panel; Complete Metabolic Panel (CMP); Complete blood count with differential (CBC w/ diff); TSH and HbA1c. Total blood volume for screen labs 14mls. Safety labs may be repeated per Investigator discretion, if needed. Blood draws may also take place at visit 2 or visit 3.

Urine collection for urinalysis.

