Maximal Oxygen Consumption (VO_{2max}). Aerobic fitness will be determined by measuring maximal O₂ consumption (VO_{2max}) during a stationary bicycle exercise test. Provider monitoring will follow The American College of Sports Medicine's (ACSM) Guidelines for Exercise Testing and Prescription and AdventHealth TRI BATS-Pilot SSP. Heart rate, blood pressure and ECG will be recorded throughout this test. During the test, participants will breathe through a low resistance mouthpiece and wear a nose clip. Expired gases will be measured by indirect calorimetry. Following a standardized warm up, participants will begin exercising at a moderate intensity with the workload (resistance on a cycle ergometer) increased every minute until the participant can no longer continue. VO₂ max tests will take as little time as possible in order to ensure that test termination is due to the participant reaching VO₂ max rather than terminating the test due to muscle exhaustion. A leveling-off (plateau) or decline in oxygen uptake should be demonstrated in order to be reasonably sure that a participant has achieved the maximum capacity for aerobic metabolism. However, there are several additional criteria that will be used to determine if maximal aerobic capacity is achieved. These criteria are: the respiratory exchange ratio (RER) increased to 1.10 or higher and the participant's heart rate increased to within 10 beats of the age-predicted maximum (208 – [0.7 x age]). This test will be supervised by a qualified Medical Provider as stated in AdventHealth TRI SOP 030.100.015 Procedural Staffing.

In the event of a positive stress test, participants are referred to their primary care physician. If the electrocardiogram (ECG) is determined to be a false negative, participant may be allowed to continue participating in the study.

Triaxial Activity Monitor: Two tri-axial accelerometer-based activity monitors will be placed during Visit 2. One will be placed on the wrist and the other on the triceps of the same arm. The monitors integrate motion sensor data from the tri-axial accelerometer to estimate the energy cost of free-living activity. The participant will wear the monitors for 5-7 days, except while showering or bathing. The participant will have the monitors removed and the data uploaded at Visit 2 or Visit 3.

Visit 2

Approximate visit time: ~ 3 hour

Review of Adverse Events, Concomitant Medications

Vital Signs

Body Weight (metabolic)

Collection of Activity Monitors

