Activity Monitoring. Participants with nickel allergies will not be required to wear the Bodymedia activity monitor.

BiodeX/Strength testing/Exercise/Maximal Oxygen Consumption (VO_{2max}). Prior to conducting any exercise testing, a history and physical including ECG will be conducted and will be used to determine whether a participant is clear to participate in exercise testing. An MD/DO/NP/PA will be available during exercise testing for participants who are at risk according to the American College of Sports Medicine (ACSM) Guidelines. ECG, blood pressure and heart rate may be monitored during the test.

Magnetic Resonance Imaging and Spectroscopy. There will be a strict safety screening protocol, to ensure any people with contraindications are excluded from volunteering. There will be no diagnostic analysis associated with any of the MR sequences used in this protocol. However, some of the MR images we obtain as part of this protocol may show incidental medical findings. In the case where a medical abnormality is apparent on an image, the image will first be reviewed by an investigator on this protocol. If the abnormality is confirmed, then the participant will be instructed to seek medical attention from their health care provider.

Hyperinsulinemic-Euglycemic Clamp. In-house supervision by a qualified physician or mid-level provider at all times during the procedure. Constant monitoring of blood glucose during the procedure (every 5-10 minutes). Immediate availability of corrective measures (IV 50% dextrose and/or glucagon).

Provisions to Protect the Privacy Interest of Participants

Participants will be assigned unique identifiers for study-related records. All precautions will be taken to make sure that only authorized individuals will access participant research records. The collection of sensitive information about participants will be limited to minimum necessary to achieve the aims of the research, so that no unneeded sensitive information will be collected.

Early Withdrawal of Participants

Investigator Withdrawal of Participants

The participation in this study may be stopped at any time by the study PI without the participant's consent because:

- The study Medical investigator thinks it necessary for participant's health or safety;
- Participant has not followed study instructions;
- The AdventHealth TRI has stopped the study; or
- Administrative reasons require the participant's withdrawal.

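### Exclusion criterion 5 and the Visit 1 VO2max procedure set conflicting conditions for continuing after a positive stress test, and must be reconciled

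*Combined protocol and SAP*

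**What the plan says.** The rule for a positive stress test appears in two places in the combined protocol and SAP.

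- **Exclusion Criteria, item 5.** After the cardiovascular exclusions, the item says: "In the event of a positive stress test, participants are referred to their primary care physician". It continues: "If the electrocardiogram (ECG) is determined to be a false positive, participant may be allowed to participate in study after confirmatory records obtained".
- **Study Procedures, Visit 1, Maximal Oxygen Consumption.** The same referral sentence appears at the end of the test description. It is followed by: "If the electrocardiogram (ECG) is determined to be a false negative, participant may be allowed to continue participating in the study".

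Other text bears on cardiac safety around exercise:

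- Item 5 excludes anyone where "participant has evidence of cardiovascular disease assessed during the ECG at screening".
- Participants Recruitment and Screening says: "Potential participants will be medically screened to determine good health and without any contraindication to exercise".
- Mitigation of Risks says that a history and physical with ECG, done before exercise testing, "will be used to determine whether a participant is clear to participate in exercise testing".
- The VO2max description says: "This test will be supervised by a qualified Medical Provider".
- The investigator may withdraw a participant for health or safety (Early Withdrawal of Participants).

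**The concern.** The two statements start from the same event and take the same first step. They then attach permission to go on to different ECG determinations, and differ on whether records are mentioned. A provider with a positive test in hand cannot satisfy both by following the text.

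At stake is a safety and continuation rule in people aged 65 to 90. The protocol's own Potential Risks section lists heart attack, stroke and death as rare risks of exercise testing. Whether a given participant stays in the study could depend on which section is consulted.

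**Working it through.** No formula applies and the plan gives no figure to reproduce. The check is a comparison of the texts.

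**Step 1. Confirm that both passages concern the same test.** The Schedule of Activities lists the VO2max test and the stress test as one row, and the study visit text places that test at Visit 1. Item 5 and the Visit 1 procedure therefore govern the same event.

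**Step 2. Set the two rules side by side.**

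| Element | Exclusion criterion 5 | Visit 1 VO2max procedure |
|---|---|---|
| Trigger | Positive stress test | Positive stress test |
| First action | Referral to primary care physician | Referral to primary care physician |
| ECG determination named | False positive | False negative |
| Confirmatory records | Required first | Not mentioned |
| Permission | May be allowed | May be allowed |

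Trigger, referral and permissive wording agree. The determination and the records requirement do not.

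**Step 3. Test whether the Visit 1 sentence can be applied.** It depends on which tracing is meant by the ECG, and the text does not say.

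- If it is the stress-test ECG, a positive result cannot be a false negative. The condition is never met, and the Visit 1 text gives no route for the participant whom item 5 could admit.
- If it is another tracing, such as the resting ECG at screening, the sentence could be read as allowing someone with a missed abnormality to continue.

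Neither reading gives the same rule as item 5.

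**Step 4. Look for text that settles the matter.**

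| Safeguard | When it acts |
|---|---|
| Cardiovascular disease on the screening ECG | At SV1, before the stress test |
| Medical screening for contraindications | At entry |
| Clearance by history, physical and ECG | Before exercise testing |
| Supervision by a medical provider | During the test |
| Investigator withdrawal for health or safety | Any time, as general discretion |

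The first three act before the stress-test result exists. Supervision covers the conduct of the test, and withdrawal is not specific to this event. The two sentences in Step 2 are the only specific text on what follows a positive result.

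**Step 5. Establish who is exposed.**

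- Phase I applies to everyone: "Both older athlete and older sedentary groups will undergo the screening and pre-intervention testing phase". Planned enrolment is 18 per group, so 18 × 2 = 36 baseline tests if all reach Visit 1.
- Both groups then have muscle power and 1-RM testing at Visit 2. The schedule puts Visit 1 at day −26 and Visit 2 at day −19, so nominally −19 − (−26) = 7 days later.
- Only OS participants train for 8 weeks and repeat the VO2max test in Phase III, whose text points back to the Phase I descriptions. With 15 anticipated completers out of 18 enrolled, that adds 15 to 18 tests.
- Test occasions in total: 36 + 15 = 51 to 36 + 18 = 54.

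The documents give no expected proportion of positive tests, so these counts cannot be turned into a number of affected participants.

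**The case against.** The strongest reply is that the protocol is not without a rule. Item 5 alone gives a full sequence of referral, determination and records. The Visit 1 text repeats the referral, and several other safeguards surround exercise testing. That stands. A reader might infer that the safety gate is undefined, but the documents do not support this: the return condition is inconsistent, within a wider gate that is defined.

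Four other inferences also go further than the text.

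- **That the two rules give opposite decisions on the same finding.** Each names a determination on which the other is silent, and both are permissive. They set incompatible conditions, but neither forbids what the other allows.
- **That the Visit 1 procedure waives confirmatory records.** It omits them. Item 5 remains in force in the same protocol.
- **That a participant with a missed abnormality would be let through.** This is only one of the two readings in Step 3.
- **That Visit 1 staff work from the Visit 1 wording.** The procedure points to outside exercise-testing guidelines and a site-specific document for provider monitoring. Neither is available here, so what staff use in practice is unknown.

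It may also be said that one sentence is a slip of the pen. The documents do not say so, and aligning that one word would still leave the difference over records. The conflict therefore survives these objections in the narrower form given here.

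**Conclusion.** The conflict is real. For one trigger the protocol names two different ECG determinations as the basis for continuing, requires confirmatory records in one place and does not mention them in the other, and contains nothing that reconciles the two. The Visit 1 condition does not fit its own trigger.

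The conflict affects any participant in either group with a positive test, out of 36 planned, and matters again at the repeat test in OS. How many that is cannot be estimated from the documents and may be few. Endpoints, sample size and analysis are untouched. The case for correcting it is that this is an operative participant-safety rule.

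The conclusion assumes that both passages are current text and that the stress test and the VO2max test are the same procedure, as the schedule indicates. It takes no position on which clinical rule is right.

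**What to change.** Reconcile the two passages into one rule, stated once, with the other place cross-referring to it. The rule should say which ECG determination permits continuation after a positive stress test, and whether confirmatory records are required first. It would help to say which ECG is meant and that the rule also covers the Phase III test. The medical investigator should set the clinical content.

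The cost is a short protocol amendment and a matching staff instruction. No change to the design, sample size or analysis is needed.

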Hyperinsulinemic-Euglycemic Clamp: The glucose clamp is the gold standard for measurement of insulin sensitivity and will be performed as previously described by our group (1, 5, 9, 10). After an overnight 8-hour fast, an intravenous catheter will be placed in the vein for infusion of insulin and glucose. A second catheter will be placed in the vein of the contra-lateral arm for blood withdrawal. After baseline blood is collected, a primed (210 mg/m²), continuous (2 mg/min/m²) infusion of [6,6-2H₂] glucose will be initiated for assessment of endogenous glucose production. A 2-step euglycemic clamp will be started with a 2-hour infusion of insulin (Humulin-R) at 15 mU/m²/min, followed by 2 hours at 40 mU /m²/min. Plasma glucose will be measured at 5-10 min intervals via NOVA StatStrip Glucose Meter. Plasma glucose will be allowed to either decrease to ~90 mg/dl or will be increased to ~90 mg/dl in each participant depending on the fasting blood glucose levels. Euglycemia (~90 mg/dL) will be maintained with a variable 20% dextrose infusion enriched with [6,6-2H₂] glucose. Rates of glucose disposal (M) and endogenous glucose production (EGP) will be calculated by non-steady-state equations based on plasma [6,6-2H₂] glucose enrichment determined by gas chromatography mass spectrometry. A baseline blood sample will be collected prior to -30 mins. Then three blood samples will be collected for determination of plasma insulin, free fatty acid (FFAs), C-Peptide, and glucose concentrations prior to the insulin infusion, and at the beginning of each steady state and every 10 minutes during the two steady state portions of the clamp which will last approximately 4 hours from the time at which the insulin infusion is initiated (-30min, -20min, -10min, 0min, +30min, +60min, +100min, +110min, +120min, +220min, +230min, and +240min). Participants will complete a 24-hour urine collection on days where hyperinsulinemic-euglycemic clamps are run. Total blood volume during this procedure will be approximately 192 mls.

Calculations: Hepatic glucose production is expected to be completely suppressed at this level of insulin, even in diabetic subjects. In this case, peripheral glucose uptake (R_d) should equal the glucose infusion rate (GINF) during steady state (the last 30 minutes of each step of the clamp) after correction for urinary glucose loss.

That is: - R_d = Steady State GINF - urinary glucose loss

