Appendix: Schedule of Activities

	Phase I: Pre-Intervention					Phase II: Intervention								Phase III: Post-Intervention					
	Screening	Baseline				V 4-7	V 8-11	V 12-15	V 16-19	V 20-23	V 24-27	V 28-31	V 32-35	Exercise Extension (prn)	V 36	V 37	V 38	V 39	
Visit	SV1	V1	V2	V3		D 0* - D 3	D 7 - D 10	D 14 - D 17	D 21 - D 24	D 28 - D 31	D 35 - D 38	D 42 - D 45	D 49 - D 52		D 56	D 60	D 64	D 70	D 71
Day	D -54	D -26	D -19	D -7	D -6														
Windows **	within 28 days of V1+2d	±2	±2	±4		CRU overnight	Wk 1	Wk 2	Wk 3	Wk 4	Wk 5	Wk 6	Wk 7	Wk 8	*Wk 9-11	+3	±2	±3	±2
OA Group	X	X	X	X	X	X/EOS	X	X	X	X	X	X	X	X		X	X	X	X/EOS
OS Group	X	X	X	X	X	X	X	X	X	X	X	X	X	X		X	X	X	X
Informed Consent	X																		
Inclusion/Exclusion Criteria	X																		
Demographics	X																		
Past Medical History	X																		
Concomitant Medication/Supplements	X	X	X	X	X	X	X	X	X	X	X	X	X	X	X	X	X	X	X
Physical Examination	X															X			
Adverse Events	X	X	X	X	X	X	X	X	X	X	X	X	X	X	X	X	X	X	X
Height	X			X													X		
Weight (metabolic)	X	X	X	X	X	X										X	X	X	X
BMI	X															X			
Waist circumference	X															X			
Vital Signs (BP, Pulse, Respiration, Temp)	X	X	X		X											X	X	X	X
ECG (12-lead)	X															X			
Study Specific Questionnaires:																			
MMSE, PASE, CHAMPS, Exercise History	X																		
Blood Collection: Lipid Panel, CMP, CBC with differential, TSH, HbA1c	X															X			
Blood Collection: EDTA Plasma (for		X															X		
Covid testing	X*		X*													X*		X*	
Urine Collection	X																		
Handgrip strength	X															X			
SPPB	X															X			
Step Test	X															X			
Dispense 3 Day Food Diary	X																X		
Collect 3 Day Food Diary			X														X		
MRI	X																X		
DEXA	X															X			
VO2max test/stress test	X															X			
Placement of Accelerometers	X																X		
Collect Accelerometers		X*	or X													X*	or X		
Echocardiogram		X														X			
1-RM Muscle Strength	X															X			
Biodex	X															X			
Blood Collection: POC Glucose (clamp prep)			X														X		
Dinner Meal Consumption			X														X		
24-hr Urine Collection					X													X	
Hyperinsulinemic-Euglycemic Clamp					X													X	
RMR/RQ					X														X

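### R_d, the numerator of the insulin sensitivity index, assumes zero endogenous glucose production, although the tracer measures it and no rule says how to use the measurement (minor)

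*Combined protocol and SAP*

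**What the plan says.** The procedure is under Visit 3 Day -6, in the Hyperinsulinemic-Euglycemic Clamp paragraph and the Calculations paragraph that follows it.

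- **Two insulin levels.** The clamp is a "2-hour infusion of insulin (Humulin-R) at 15 mU/m²/min, followed by 2 hours at 40 mU /m²/min".
- **Tracer measurement.** Labelled glucose is infused in order to assess EGP, and "Rates of glucose disposal (M) and endogenous glucose production (EGP) will be calculated by non-steady-state equations" from plasma enrichment.
- **Premise.** Calculations states that "Hepatic glucose production is expected to be completely suppressed at this level of insulin, even in diabetic subjects". The level is referred to in the singular.
- **Definition of R_d.** On that premise R_d "should equal the glucose infusion rate (GINF) during steady state (the last 30 minutes of each step of the clamp"), after a urinary correction. The formula line is "R_d = Steady State GINF - urinary glucose loss".
- **Use of R_d.** S_I is R_d divided by the rise in insulin from its basal level. The steady-state insulin in that denominator is the average over the last 40 minutes of the clamp.
- **GDR.** The glucose disposal rate is given a unit (per kg of fat-free mass per minute) but no statement of which disposal estimate it uses.

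Research Design lists the clamp as the measure of whole-body insulin sensitivity. Study Outcome Measures (Endpoints) names no clamp measure and covers it only through a general reference to all phenotype data. The Statistical Analysis Plan names none of S_I, R_d, M or EGP.

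**The concern.** The plan measures EGP and then defines its sensitivity index as though EGP were known to be zero. The sentence leading to the formula is worded as an expectation, but the formula itself is unconditional. These documents do not say how suppression is to be checked, or what to do if the tracer shows that it was incomplete. Because the definition covers each step, it applies to the 15 mU step as well as the 40 mU step.

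Interpretation is at stake. R_d is meant to represent peripheral glucose uptake. If residual EGP differs between older athletes and older sedentary participants, or changes with training in the sedentary group, part of that hepatic difference is booked as peripheral. The plan also leaves two disposal estimates from one clamp, the tracer-derived M and the infusion-based R_d, with no statement of how they relate. The choice between them could then be made after the data are seen.

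**Working it through.** There is no stated figure to reproduce. The check is a steady-state mass balance, followed by illustrative sizes.

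**1. Mass balance.** Let G be total exogenous glucose (dextrose plus infused tracer), E residual EGP and U urinary loss.

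- Peripheral uptake: R_d = G + E − U
- Plan's formula: R_d = G − U, if infused tracer is counted in GINF
- Error: (G − U) − (G + E − U) = −E

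The formula is exact only when E = 0. The insulin denominator is the same either way, so plan S_I / EGP-inclusive S_I = 1 − E/R_d.

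**2. Comparisons.** For a group difference or a pre-post change, the formula gives the true difference in R_d minus the difference in E. The error cancels if E is equal on both sides. No document gives E by group or time point, so no direction can be stated.

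**3. Which step S_I uses.** The last insulin samples listed are at "220min, +230min, and +240min". These are the only listed samples in the last 40 minutes of the clamp (200 to 240 min), and all lie in the 40 mU step. They are also the only ones in the last 30 minutes (210 to 240 min). The difference between the 30-minute window for infusion rate and the 40-minute window for insulin therefore has no effect on the listed insulin samples. S_I reads as a 40 mU-step value, although the text does not say that R_d must come from that step.

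**4. Size at the 40 mU step.** Assumed: E from 0 to 0.3 and R_d of 5 or 8 mg/kg/min.

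| Assumed R_d | E = 0 | E = 0.3 |
|---|---|---|
| 5 | 0% | 0.3/5 = 6.0% too low |
| 8 | 0% | 0.3/8 = 3.75%, about 3.8% too low |

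The same percentages apply to S_I.

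**5. Size at the 15 mU step.** Assumed: E from 0 to 1.0 and R_d of 3.0 mg/kg/min. The error runs from 0% to 1.0/3.0 = 33%. This R_d does not enter S_I on the reading in step 3.

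**6. Infused tracer.** The planned continuous rate is 2 mg/min/m². For assumed body sizes of 2.1 m² at 100 kg and 1.6 m² at 60 kg, this is 2 × 2.1/100 = 0.042 and 2 × 1.6/60 = 0.053 mg/kg/min. The documents do not say whether GINF counts it. If it does not, the formula is lower by about that amount again; the upper figure at R_d 5 becomes (0.3 + 0.053)/5 = 7.1%.

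**The case against.** The strongest reply is that the measurement which avoids the assumption is already planned. M and EGP both come from the tracer, and the R_d paragraph is worded conditionally. That is right: what is missing is a link between planned quantities. But S_I is defined on the infusion-based R_d, and nothing says that M replaces it.

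Second, S_I reads as a 40 mU-step index, where suppression is likely to be fuller, and Exclusion Criteria removes participants with self-reported diabetes. This stands and limits the size. A reader might infer from the 15 mU figures that S_I could be wrong by a third; the documents do not support that, because the low-step R_d does not enter S_I as it reads.

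Third, the clamp is said to follow previously described methods, with four citations. Those may contain a rule for incomplete suppression or for counting tracer. They cannot be checked here, so the claim is only that these documents state no such rule.

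Fourth, tracer-derived R_d is not error-free. With an assumed 3 to 5% tracer error, the error is 0.15 to 0.25 mg/kg/min at R_d 5 and 0.24 to 0.40 at R_d 8, comparable to the bias removed. This stands as a cost. Random error averages out across participants, whereas an omitted EGP term always lowers R_d.

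Two other stronger readings should be resisted. A reader might infer that GDR and S_I rest on conflicting disposal estimates; the text gives GDR only a unit, so this is unknown. A reader might also infer that a step-specific urinary correction is impossible, because the plan says "Participants will complete a 24-hour urine collection on days where hyperinsulinemic-euglycemic clamps are run". The documents do not say whether that collection is pooled or divided, so the most that can be said is that the timing of the correction is not specified.

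**Conclusion.** The point holds as a minor one. The stated formula omits a quantity that the study measures, applies to both steps on an expectation about one unspecified insulin level, and has no stated alternative if suppression is incomplete. R_d is understated by exactly the residual EGP at steady state, and by nothing if suppression is complete and tracer is counted.

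For S_I, read as a 40 mU-step value, the understatement is 0 to 6% on assumed EGP of 0 to 0.3 and R_d of 5 to 8 mg/kg/min, and is likely small. For R_d at the 15 mU step it is 0 to 33% on assumed EGP of 0 to 1.0 and R_d of 3.0, outside S_I. All these inputs are assumptions.

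The documents do not support saying that the comparison of athletes with sedentary participants, or the training effect, is biased in any particular direction, or that it is biased at all. They show only that hepatic and peripheral effects could be mixed. The consequence is limited further because no clamp measure is named in the endpoint list or the Statistical Analysis Plan.

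**What to change.** In the Calculations paragraph:

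1. Calculate R_d at each step from the planned tracer data. At steady state this is total exogenous glucose, including infused tracer, plus measured EGP, with urinary loss subtracted to give peripheral uptake.
2. Use this R_d in S_I, and state that R_d and insulin both come from the 40 mU step.
3. State whether GDR uses the same value.
4. Report EGP by step, so that the expectation of suppression can be checked.
5. Keep the infusion-only R_d as a labelled sensitivity result.

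The cost is a few sentences and a little more calculation from enrichment and insulin samples already planned. Tracer-derived R_d brings its own measurement error, which is the reason for keeping the infusion-only value. No visit, sample, primary comparison or sample size changes.
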